## **SUMMARY OF PROTOCOL VERSIONS AND CHANGES**

### **Version 1.0**

- Original version approved by the Marcus Institute, Hebrew SeniorLife Review Board on May 13th, 2018.

### **Version 1.1**

- Changes to consent, recruitment, protocol on June 28, 2019.

### **Version 1.2**

- Changes to protocol approved on July 26th, 2019.

### **Version 1.3**

- Minor changes to previously approved forms approved on August 23rd, 2019.

### **Version 1.4**

- Changes to the recruitment documents approved on August 28th, 2019.

### **Version 1.5**

- Changes in the protocol on September 30th, 2019.

### **Version 1.6**

- Changes in the protocol on October 23rd, 2019.

### **Version 1.7**

- Approval of the incident report on October 24th, 2019.

### **Version 1.8**

- Submission of protocol and final statistical analysis plan to the IRB on October 29th, 2019.

## SYNOPSIS

Elevated blood pressure (BP) affects virtually all adults over the age of 65 years in the United States and is a risk factor for both cardiovascular events and falls, which are common causes of long-term disability and premature death. Many older adults have limited mobility and experience food insecurity, relying on others for food preparation. Further, meals prepared for older adults are often high in sodium to overcome age-related declines in taste. Because of this, the Centers for Disease Control declared reduced-sodium meal plans in congregate living facilities a priority to combat the hypertension epidemic among older adults. However, many dietitians and health practitioners worry that low sodium in older adults could result in orthostatic hypotension (OH), causing impairments in physical function and consequently falls. Beyond BP there is evidence that sodium intake directly influences balance, seated-to-standing transitions, and gait speed. However, to date there are no clinical trials of the effects of sodium reduction on physical function.

We intend to perform an individual level randomized clinical trial at a community-based, congregate senior living facility that compares a reduced sodium meal plan (<0.9 mg per kcal of energy intake) to their typical meal plan (~2 mg per kcal of energy intake). This proposal has the following aims: (1) to determine the short-term effects of sodium reduction on BP regulation and OH, a hypothesized mechanism by which sodium intake might affect physical function; (2) to determine the short-term effects of a reduced sodium diet on physical function; and (3) to establish the premise for a longer-term trial by examining diet compliance, tolerability, and palatability. Ultimately, our two-tailed hypothesis ensures a high impact result long-term, since no effect on physical function would reinforce the safety of sodium reduction for cardiovascular disease prevention, while a positive relationship would reinforce a cautious approach to sodium reduction in this population. Beyond our scientific aims, our proposal will result in the development of a reduced sodium meal plan, using the leading food industry design platform, which can be readily implemented in a standardized fashion at long-term, senior care facilities throughout the country.

This pilot proposal will inform a clinical trial of sodium reduction in the prepared meals of semi-independent older adults. By demonstrating the impact of sodium reduction on fall risk factors like physical function and OH, our study will provide pertinent and timely guidance as to how sodium content in meals prepared for seniors impacts risk for clinical events that have long-term implications for independence.

**Study Title:** The Effect of Sodium Reduction on Blood Pressure and Physical Function in Older Adults (SOTRUE)

## Objectives

*Specify the primary and secondary objectives.*

Virtually all older adults have hypertension, a known contributor to both cardiovascular disease and falls. The Centers of Disease Control has advocated for low sodium, senior meal plans as a strategy to lower BP.(1) However, the long-term effects of low sodium intake on physical function are largely unknown in older adults. Our pilot proposal for a randomized feeding study of a low sodium meal plan in a community-based, congregate senior living facility, will not only establish the premise for a definitive long-term trial on sodium reduction and physical function in older adults, but further contribute to a translatable, standardized menu that can be implemented *en masse* at senior living facilities throughout the U.S. Our long-term goal is to discover dietary interventions that enhance physical function as adults age. The objective of this proposed pilot study is to determine the feasibility of an individual-level, randomized feeding study that examines the impact of sodium reduction on BP regulation among semi-independent, older adults. Our central hypothesis is that sodium reduction will reduce seated BP without causing OH. Improved BP regulation will enhance circulatory function, efficiency of dynamic transitions from seated to standing positions, and ultimately a lower risk of falls.

**Primary Aim 1:** To determine the effects of a low sodium (<0.9 mg per kcal of energy intake), 2-week meal plan compared with a usual meal plan (average sodium ~2 mg per kcal of energy intake) on seated BP among independently living older adults.

**Hypothesis Aim 1:** *Compared with the usual meal plan, a reduced sodium meal plan will lower seated BP in older adults after 2 weeks.*

**Feasibility Aim 1:** To evaluate the recruitment experience, meal cost, meal delivery logistics, and compliance with and tolerability of the meal plan (urine sodium and palatability questionnaires).

**Feasibility Aim 2:** To determine effect size (variance) of secondary outcomes: standing BP, OH (standing minus seated BP), orthostatic symptoms, and a timed up and go test (TUG).

## Design and Outcomes

This study is an individual-level, parallel, randomized clinical trial. Eligible participants will be randomized to low versus usual sodium meal plans for two weeks. Assessments will be made at the in-person baseline visit, one week telephonic interview and 2 week in person follow-up visit. This proposal will be executed in collaboration with Dietetic Services of the Jack Satter House (Revere), which is equipped with an industry-grade kitchen, chefs, and in-person dining as well as delivery services that collectively serve 255 residents. Further, the facility has private space for interviews and assessments. We plan to recruit 40 individuals (75% women).

## **Interventions and Duration**

Interventions for this study include:

1. A low sodium diet
2. A usual sodium diet

A participant will be on one of these two intervention arms for a period of 2 weeks. The last study visit for each participant will occur on the last day of their study diet intervention.

## **Sample Size and Population**

Study participants will include residents of Jack Satter House in Revere who are aged 60 years and older. Forty men and women will be enrolled in this study. Participants will be randomized using a computer-generated randomization scheme with varying sized blocks to 1 of 2 sequences in a 1:1 ratio such that approximately half of participants will undergo the low sodium diet intervention first or usual sodium diet intervention.

## 1 STUDY OBJECTIVES

### 1.1 Primary Objective

**Primary Aim 1:** To determine the effects of a low sodium (<0.9 mg per kcal of energy intake), 2-week meal plan compared with a usual meal plan (average sodium ~2 mg per kcal of energy intake) on seated BP among independently living older adults.

***Hypothesis Aim 1:** Compared with the usual meal plan, a reduced sodium meal plan will lower seated BP in older adults after 2 weeks.*

### 1.2 Secondary Objectives

**Feasibility Aim 1:** To evaluate the recruitment experience, meal cost, meal delivery logistics, and compliance with and tolerability of the meal plan (urine sodium and palatability questionnaires).

**Feasibility Aim 2:** To determine effect size (variance) of secondary outcomes: standing BP, orthostatic hypotension (OH, standing minus seated BP), orthostatic symptoms, and a timed up and go test (TUG).

## 2 BACKGROUND AND RATIONALE

### 2.1 Background on Condition, Disease, or Other Primary Study Focus

#### Significance

Hypertension is rampant among older adults and is a major contributor to cardiovascular disease, falls, and early death. Healthy diet is a critical determinant of BP, and decline in diet quality is a common precursor to decline in global health. High sodium intake contributes to high blood pressure (BP), nevertheless, *9 of 10 Americans consume an excessive amount of dietary sodium each day*.(2) Older adults with mobility limitations rely on others to prepare their foods, which are often high in sodium to combat age-related declines in taste. Efforts to reduce sodium in senior meal plans have been stymied by conflicting evidence about its health effects, summarized below.

**1. Both hypertension and OH are fall risk factors.** Uncontrolled high BP is a potent risk factor for falls among older adults.(3) Age-related hypertension results from vascular stiffness, decreased baroreceptor sensitivity, and altered sodium metabolism, contributing to low BP with changes in posture, called OH.(4, 5) These acute drops in BP impair physical function. In our own studies, OH was associated with postural light-headedness, dizziness, and falls.(6-8) In other studies, OH was strongly associated with impaired static (e.g. balance upon standing) (9) and dynamic physical performance (e.g. chair stands, TUG, and 4m gait speed).(10, 11)

**2. Sodium is recommended to treat OH, but also worsens hypertension.** While multiple studies have demonstrated improved orthostatic tolerance with sodium supplementation,(12-15) a 2017 consensus statement highlighted a need for long-term evidence, stating that the “long-term risks associated with greater salt intake...need to be weighed against the short-term risks

of...OH resulting in fall injury...the long-term risks of high sodium diets in individuals with OH have not been well studied.”(16, 17)

**3. Sodium reduction lowers BP with unknown effects on physical function.** Intensive pharmacologic treatment to lower BP reduces risk of OH without increasing risk of falls long-term.(18-20) Moreover, the Trial of Nonpharmacologic Interventions in the Elderly (TONE) study, established sodium reduction as an efficacious, non-pharmacologic intervention to lower BP in older adults.(21) Whether reduced sodium reduced OH, improved physical function, or prevented falls was not reported. Nevertheless, several studies observed that long-term sodium reduction increased orthostatic tolerance in rats (22) and had no effect on orthostatic tolerance in astronauts.(23) In data from the DASH-Sodium trial,(24) we found that reduced sodium in the context of a healthy diet, actually decreased orthostatic light-headedness.(25)

## 2.2 Study Rationale

Interventional studies supporting sodium reduction have largely been performed in middle-aged adults. Furthermore, sodium reduction is controversial in older adults, (26) due to concerns about OH, which is highly prevalent among older adults and potentially worsened by low sodium. This debate is perpetuated by observational studies that have described a higher risk of mortality among adults consuming a low sodium diet. In contrast, multiple studies have shown that higher sodium consumption increases BP and causes lightheadedness. Furthermore, trials of BP management have demonstrated that lower BP decreases risk of OH without increasing the risk of falls. Given the controversies surrounding sodium reduction, there has been a call for a definitive clinical trial from institutions worldwide, including: the Institutes of Medicine, the World Heart Federation, the European Society of Hypertension, and the European Public Health Association.(26) One of the challenges facing prior studies of sodium reduction is achieving a controlled environment, (21, 27, 28) especially among free living people. This has led some experts to suggest a population of prisoners, nursing home residents, or military personnel as ideal for a sodium trial.(26) However, ethical concerns, confounding medical conditions, or physical exertion requiring higher sodium are concerns in these populations. ***Our approach of recruiting older adults, who participate in a meal plan of a congregate housing facility of HSL overcomes the above limitations, creating a controlled environment with the opportunity for a long-term intervention.***

## 3 STUDY DESIGN

- This is a placebo-controlled, double-blinded randomized controlled trial.
- Primary outcome includes seated blood pressure and secondary outcomes include orthostatic hypotension and timed up-and-go test.
- The study includes two arms (1) Low sodium meal plan and (2) Usual sodium meal plan. Forty participants will be enrolled in the study.
- Study population includes older men and women residing in the Jack Satter House, a congregate housing facility in Revere. Approximate duration of enrollment period and follow-up (specify individual participant vs. entire trial)

- After baseline data collection, participants will be randomized in a 1:1 ratio to 1 of 2 meal plans: a usual meal plan (this is the current meal plan with an average sodium intake of 2g per kcal of energy intake) or a low sodium meal plan (<0.9 g per kcal of energy intake similar to levels recommended by the American Heart Association recommendations). Both normotensive and hypertensive individuals will be recruited. Hypertension treatment will be considered as a pre-specified stratification variable.
- Urine will be collected from a random void at the baseline and follow up visits to measure sodium, potassium, and random creatinine. The samples will be sent to Quest Diagnostics Laboratories for analysis to measure excretion of these minerals pre and post exposure to the study diet. For urinary sodium the methodology used is ion selective electrode, with a reference range of 28 to 272 mmol/L. For urinary potassium sodium the methodology used is ion selective electrode, with a reference range of 12-129 mmol/L. For random urinary creatinine the methodology is kinetic colorimetry with a reference range for males of 20-320 mg/dl and females of 20-275 mg/dl.
- Quest Diagnostics is a nationally recognized CLIA certified laboratory capable of accurate and reproducible results on the analyses above. Reports are available electronically and will be uploaded directly into the statistical software at HSL via a CSV file.

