### **9.2 Sample Size and Randomization**

To detect the difference in seated SBP observed in the DASH-Sodium trial at 2-weeks (-9.53 mm Hg, standard deviation of 10.46, a type 1 error of 0.05 with 80% power), we would need 20 people in both arms (total 40). We will recruit 45 participants to account for a 10% attrition rate. Effect and variance data from the other endpoints will be used for sample size calculations in subsequent proposals.

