1.1 Primary aim

To determine the effects of a low sodium (<0.9 mg per kcal of energy intake), 2-week meal plan compared with a usual meal plan (average sodium ~2 mg per kcal of energy intake) on seated BP among independently living older adults. In this randomized controlled trial (RCT) of 45 patients, we will compare a low sodium diet intervention vs. usual sodium diet over 2 weeks to determine the effect of the sodium reduction on seated blood pressure.

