3.2 Power and sample size

To detect the 2-week difference in seated SBP (primary outcome) observed in the DASH-Sodium trial² (-9.53 mm Hg, standard deviation of 10.46, a type 1 error of 0.05 with 80% power), we need 20 people in each arm (total 40). We will recruit 45 participants to account for a 10% attrition rate. Effect size and variance for the other endpoints (especially OH) will be used to inform power calculations for subsequent proposals.

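### Three protocol sections set enrolment at 40, but the sample-size section and the SAP need 45 to keep 40 after 10% attrition; 40 enrolled with that attrition gives about 76% power, not 80%.

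*Protocol*

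**What the plan says.** Three places in the protocol put the number recruited or enrolled at 40:

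- Synopsis, Design and Outcomes: "We plan to recruit 40 individuals (75% women"
- Synopsis, Sample Size and Population: "Forty men and women will be enrolled in this study"
- Section 3, Study Design: "Forty participants will be enrolled in the study"

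Protocol section 9.2 gives 20 per arm, 40 in total, as the number needed for 80% power, and then adds an allowance for loss: "We will recruit 45 participants to account for a 10% attrition rate". SAP 3.2 repeats both figures. The SAP introduction also describes the trial as one of 45 adults, and SAP 1.1 begins its description of the comparison with "In this randomized controlled trial (RCT) of 45 patients".

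Protocol section 4.3 states that the entire cohort will be recruited before the intervention begins.

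**The concern.** The documents give two enrolment targets for one trial. A distinction between people recruited and people evaluable does not explain the gap. The synopsis and section 9.2 both speak of recruiting, one with 40 and the other with 45, and the other two places say enrolled. None of these statements belongs to the version history, so all are current text.

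The sections that say 40 present the number needed at analysis as the number to enrol, which leaves no allowance for the attrition the plan itself expects. Because recruitment closes before feeding starts, the target is fixed before any dropout during the intervention is known, and the plan describes no replacement. Staff who work from the design section would stop five people short of what section 9.2 requires, and the power claim for the primary outcome would no longer match the trial being run.

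**Working it through.** **Inputs.** Protocol 9.2 gives the difference (negative, i.e. a fall), SD, alpha and power: "9.53 mm Hg, standard deviation of 10.46, a type 1 error of 0.05 with 80% power". SAP 3.2 states the same values. Allocation is 1:1 (section 3), and the primary test in protocol 9.5 is two-sided at 0.05. Attrition is 10% (section 9.2 and SAP 3.2).

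**Step 1: reproduce 20 per arm.** By the normal approximation,

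n per arm = 2 × [SD × (1.960 + 0.842) / difference]² = 2 × [10.46 × 2.802 / 9.53]² = 18.9, so 19.

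The two-sample t-test uses noncentrality difference / (SD × √(2/n)) with 2n − 2 degrees of freedom:

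| n per arm | Noncentrality | df | Power, two-sided 0.05 |
|---|---|---|---|
| 18 | 2.733 | 34 | 75.7% |
| 19 | 2.808 | 36 | 78.0% |
| 20 | 2.881 | 38 | 80.2% |

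Twenty per arm is the smallest size that reaches 80%. The plan's figure therefore reproduces exactly with the t-test.

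**Step 2: reproduce 45.** 40 / (1 − 0.10) = 44.4, rounded up to 45. This also matches.

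**Step 3: apply the same attrition to each target.**

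| Enrolled | Left after 10% loss | Power, t-test | Power, normal approximation |
|---|---|---|---|
| 45 | 45 × 0.9 = 40.5, about 20 per arm | 80.2% | 82.2% |
| 40 | 40 × 0.9 = 36, 18 per arm | 75.7% | 78.0% |

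If the four losses all fell in one arm (20 against 16), t-test power would be 75.1%.

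**Step 4: no attrition.** With 40 enrolled and all 40 analysed, power is 80.2% by the t-test, which meets the target with almost no margin.

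**The case against.** The strongest reply is that the intended number is clear and the loss is small. The section that derives the sample size, the matching SAP section and two further SAP statements all say 45. The 40 appears only in summary and overview text, so a careful reader could settle the matter, and under-enrolment is possible but not shown. The trial is also a two-week pilot with feasibility aims, and it encourages follow-up after discontinuation. These points limit the consequence. They do not remove the contradiction, and the plan does make a formal power claim for its primary outcome.

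Three technical points bear on the size of the shortfall:

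- **It depends on attrition.** Full retention of 40 gives 80.2%, so the claim holds only under the plan's 10% loss. That assumption is the plan's own.
- **The primary model adjusts for baseline blood pressure, and the figures above do not.** The documents give no baseline to follow-up correlation and do not say whether 10.46 is the SD of a change. Suppose 10.46 is the SD of follow-up SBP, so that adjustment multiplies it by √(1 − r²). Then 18 per arm gives about 77% at r = 0.2, 79% at r = 0.3, 82% at r = 0.4 and 87% at r = 0.5. If 10.46 already reflects change or adjustment, there may be no such gain. The plan cannot rely on it as written.
- **SAP 3.1 tests the primary outcome at 0.25.** At that level 18 per arm gives about 94% power. However, both sample-size sections state 0.05, so that is the basis for checking their 80%. The conflict between the two alpha levels is a separate matter.

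**Conclusion.** The concern holds. Section 9.2 and the SAP are arithmetically right, and the three statements of 40 contradict them. Under 10% attrition, two-sided alpha 0.05, a difference of 9.53 mm Hg, SD 10.46 and an unadjusted comparison, enrolling 40 leaves 36. Power is then 75.7% by the t-test, about 4 points below the stated 80%, or 78.0% by the normal approximation, about 2 points below. The t-test figure is the better guide because it is the method that returns exactly 20 per arm. Baseline adjustment could close the gap, but the documents do not allow that gain to be calculated. The inconsistency stands whatever weight is given to the power loss, and it should be corrected.

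**What to change.** In both synopsis sections (Design and Outcomes; Sample Size and Population) and in section 3, replace 40 with 45 enrolled, to give 40 evaluable after 10% attrition. This changes wording only, because 45 is already the planned figure in section 9.2 and the SAP.

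If enrolment is really capped at 40, keep those sections and change the others. Section 9.2 and SAP 3.2 should then drop the target of 45 and state power of about 76% for 36 analysed under 10% attrition. The 45 in the SAP introduction and SAP 1.1 should also be corrected. The cost of this route is a slightly less favourable power statement.

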Randomization procedure: After baseline data collection, participants will be randomized in a 1:1 ratio to 1 of 2 meal plans: a usual meal plan or a low sodium meal plan. Randomization will be achieved using a web-based, password-protected, randomization software. While trial participants will know their intervention assignments, investigators and all study staff involved in baseline and follow-up data collection will be masked to participants' randomization assignments. Study staff involved in administering the dietary intervention and assessing compliance will be masked to participants' BP measurements. We will recruit the entire population cohort prior to initiating the intervention.

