#### **9.2.1 Treatment Assignment Procedures**

Participants will be randomized using a computer-generated randomization scheme with varying sized blocks to 1 of 2 sequences in a 1:1 ratio such that approximately half of participants will undergo the low sodium diet intervention, while the other half will undergo the usual sodium meal

plan intervention. Sex will be used as a stratification variable to ensure that sex is evenly distributed between interventions.

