#### **Secondary Pre-specified Subpopulations Analysis**

We will repeat the primary analysis to compare subpopulations based on the following criteria:

1. Baseline antihypertensive use (yes vs no)
2. Baseline diabetes (yes vs no)
3. Sex (men or women)

We will fit general linear models including a subpopulation of interest as a main effect term and an interaction with treatment term. The interaction terms will be used to assess for effect modification by baseline characteristic. Note these analyses are contingent on having sufficient number of participants with and without baseline antihypertensive use. Other stratified or subpopulations analyses based on baseline characteristics may be performed for hypothesis generation beyond the main study.

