SOTRUE

STATISTICAL ANALYSIS PLAN

VERSION 1.0

October 29, 2019

Table of Contents

1	Introduction.....	3
	Primary aim.....	3
	Other aims.....	3
2	Data Source.....	4
3	Primary Outcome: Serum Uric Acid.....	5
	Randomization and primary analysis.....	5
	Power and sample size.....	5
	Pre-specified Stratified Analysis.....	5
	Sensitivity analyses.....	6
4	Other outcomes	6
	Analysis	6
5	Missing data.....	8
6	Safety outcomes	9
7	References.....	10

1 Introduction

SOTRUE is an individual level, randomized feeding trial to determine the effect of 2 weeks of low sodium meal plan on seated blood pressure in 45 adults over the age of 60 years. Participants are randomly assigned to one of 2 meal plans: (1) Low sodium meal plan or (2) usual meal plan.

The **primary outcome** is the net effect of reduced sodium versus usual diet on 2-week seated blood pressure.

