3.1 Randomization and primary analysis

Participants will be randomized using a computer-generated randomization scheme with varying sized blocks to 1 of 2 meal plans in a 1:1 ratio such that approximately half of participants will undergo the low sodium diet intervention, while the other half will undergo the usual sodium meal plan intervention. Sex will be used as a stratification variable to ensure that sex is evenly distributed between interventions.

We will first confirm that the residuals of seated blood pressure are normally distributed (if not then it will be log-transformed). We will compare net effect of reduced sodium versus usual diet on 2-week seated blood pressure. This comparison will be performed by fitting a linear regression model with adjustment for baseline seated blood pressure. We will perform an intent-to-treat analysis.

Our hypothesis is that 2-weeks of a low sodium meal plan intervention will lower seated blood pressure compared to 2-weeks of a usual sodium diet. The null hypothesis is that there will be no difference in seated blood pressure between the two intervention arms. The comparison between the two treatment groups will be performed by comparing the regression coefficient for treatment with zero (two-sided Wald test at 0.25 significance level to avoid type II error)¹ using linear regression with adjustment for baseline blood pressure.

Our primary outcome will be the average of two systolic blood pressures measured on days 12-15 of the study period. A sensitivity analysis will be performed examining the last systolic blood pressure measurement.

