3.3 Secondary Pre-specified Subpopulations Analysis

We will repeat the primary analysis to compare subpopulations based on the following criteria:

1. Baseline antihypertensive use (yes vs no)
2. Baseline diabetes (yes vs no)
3. Sex (men or women)

We will fit general linear models including a subpopulation of interest as a main effect term and an interaction with treatment term. The interaction terms will be used to assess for effect modification by baseline characteristic. Note these analyses are contingent on having sufficient number of participants with and without baseline antihypertensive use.

Other stratified or subpopulations analyses based on baseline characteristics may be performed for hypothesis generation beyond the main study.

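### Protocol section 3 calls hypertension treatment a stratification variable, but the allocation scheme stratifies by sex only and the primary model adjusts for neither factor

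*Protocol*

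**What the plan says.** Protocol section 3 describes 1:1 randomisation to the two meal plans, says that people with and without hypertension will be recruited, and ends the same bullet with "Hypertension treatment will be considered as a pre-specified stratification variable".

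Protocol 9.2.1, which specifies the computer-generated list with varying blocks, says "Sex will be used as a stratification variable to ensure that sex is evenly distributed between interventions". SAP 3.1 repeats that sentence. Neither names a second factor. Protocol 4.3 ("Randomization will be achieved using a web-based, password-protected, randomization software") and the Randomization paragraph of 6.2.2 give no stratification factor at all.

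Baseline antihypertensive use is the first of three subgroup factors in Protocol 9.5 and SAP 3.3; sex is the third. SAP 3.3 adds: "Note these analyses are contingent on having sufficient number of participants with and without baseline antihypertensive use". Medication changes after randomisation also define one of the on-treatment sensitivity analyses. The primary comparison is made by "fitting a linear regression model with adjustment for baseline seated blood pressure", with no other covariate.

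**The concern.** The same term, stratification variable, is attached to hypertension treatment in one section and to sex in the two sections from which the list would be built. A programmer or an independent reader cannot tell from the documents whether treatment status was meant to be a randomisation stratum.

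The question matters because the outcome is blood pressure and the plan itself singles out treatment status as important. With about 20 people per arm, a factor left out of the list can end up unevenly split by chance. The primary model would not correct for such a split, except through whatever part baseline seated pressure already captures.

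**Working it through.** **The planned sample size, for reference.** Protocol 9.2 and SAP 3.2 plan on "9.53 mm Hg, standard deviation of 10.46, a type 1 error of 0.05 with 80% power". Taking the test as two-sided:

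- Normal approximation: n per arm = 2 × (1.960 + 0.842)² × (10.46/9.53)² = 18.9, so 19.
- Two-sample t-test: 19.92, so 20 per arm and 40 in total.
- Attrition: 40/0.90 = 44.4, so 45.

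The stated 20, 40 and 45 reproduce. The point below does not dispute them, and adding a stratum would not change them.

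**The sections side by side.**

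| Place | Factor named |
|---|---|
| Protocol 3 | Hypertension treatment |
| Protocol 4.3 and 6.2.2 | None |
| Protocol 9.2.1 | Sex |
| SAP 3.1, randomisation | Sex |
| Protocol 9.5 and SAP 3.1, primary model | Baseline seated blood pressure only |
| Protocol 9.5 and SAP 3.3, subgroups | Antihypertensive use, diabetes, sex |

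**Chance imbalance if treatment status is not a stratum.** The documents give no prevalence of antihypertensive use, so 50-80% is assumed. With K treated among N people and arm sizes a and N − a, the number treated in the first arm, k, is hypergeometric. The gap between arms is |k/a − (K − k)/(N − a)|. Blocking and the sex strata are ignored.

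| Assumed treated | K of 40 | Gap ≥20 points, 20 v 20 | Gap >20 points, 20 v 20 | K of 45 | Gap ≥20 points, 23 v 22 |
|---|---|---|---|---|---|
| 50% | 20 | 34.3% | 11.3% | 22 | 13.9% |
| 60% | 24 | 33.3% | 10.5% | 27 | 13.0% |
| 70% | 28 | 30.1% | 8.2% | 31 | 10.8% |
| 80% | 32 | 23.5% | 4.4% | 36 | 13.5% |

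Much of the difference between the two arm sizes comes from the cut-off. At 20 v 20 with these K, gaps move in steps of 10 points, so 14 against 10 treated is exactly 20 points and is counted. At 23 v 22, 16/23 against 11/22 is 69.6% − 50.0% = 19.6 points and is not counted.

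**What balance would do for the subgroup analysis.** The standard error of the treatment-by-use interaction is 10.46 × √(sum of 1/n over the four cells). At N = 40:

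- 50% treated, balanced: 10.46 × √(4/10) = 6.6 mm Hg.
- 80% treated, balanced: 10.46 × √(2/16 + 2/4) = 8.3 mm Hg.
- Averaged over unstratified allocations: about 6.7 and 8.7 mm Hg respectively.

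The interaction detectable with 80% power at two-sided 0.05 is 2.80 times the balanced standard error, about 18.5 to 23 mm Hg. That is roughly twice the planned 9.53 mm Hg main effect. Stratifying would mainly guard against a sparse cell: at 80% treated and N = 40, some arm-by-use cell has two or fewer people in about 24% of unstratified allocations.

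**The case against.** The strongest reply is that section 3 was never about the list. It calls hypertension treatment a variable that will be considered, not the one that will be used, and the sentence just before it concerns recruitment. The SAP contents page lists "Pre-specified Stratified Analysis" for what the body calls a subpopulations analysis, and antihypertensive use comes first there. On that reading the two allocation sections agree with each other and section 3 needs only a clarifying phrase. This reading is possible and cannot be excluded. It does not remove the point: section 3 does not say it, 9.2.1 uses the same term for a randomisation stratum, and the factor is still unbalanced by design and absent from the primary model.

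Three stronger inferences are tempting, and the documents do not support them.

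- **That imbalance is likely.** At a 20-point gap it is a minority outcome throughout the assumed range, and at 23 v 22 it occurs in only about 11-14% of allocations.
- **That the estimate would move by 1-2 mm Hg.** This needs a difference of 5-10 mm Hg between treated and untreated people that remains after adjustment for baseline pressure (0.20 × 5 to 10). Nothing in the documents supplies that figure. Eligibility also restricts systolic pressure to 100-149 mm Hg and requires stable medication. A shift of that size would lie within the standard error of the difference, 10.46 × √(2/20) = 3.3 mm Hg.
- **That the subgroup analysis fails for want of stratification.** The SAP 3.3 condition concerns how many users and non-users are enrolled, and stratified allocation does not change those totals.

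Stratifying on sex alone in 40-45 people is also a defensible choice.

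**Conclusion.** The inconsistency is real and should be resolved. Protocol section 3 names a factor that the allocation sections omit, and the primary model adjusts neither for that factor nor for sex, the stratum that is used.

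The consequence is moderate. Randomisation is sound, the primary test is valid and unbiased in expectation, and the sample size stands. What remains is exposure to an unlucky split: about 24-34% of allocations at 20 v 20 for a gap of 20 points or more (4-11% for a larger gap), and about 11-14% at 23 v 22. These figures rest on the assumed 50-80% prevalence and on ignoring blocks and sex strata. The size of any resulting shift in systolic pressure cannot be determined from the documents.

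**What to change.** 1. Make Protocol section 3, Protocol 9.2.1 and SAP 3.1 name the same randomisation factor or factors, namely those actually used in the list. If section 3 meant only the subgroup analysis, reword it to say so.
2. In Protocol 9.5 and SAP 3.1, pre-specify baseline antihypertensive use (yes/no) and sex as covariates beside baseline seated blood pressure in the primary linear model. The medication list is taken at Visit 1, and both variables are already needed for SAP 3.3. The cost is two degrees of freedom: with 40 people analysed, residual degrees of freedom fall from 40 − 3 = 37 to 40 − 5 = 35.
3. Stratifying the list on antihypertensive use as well is optional, and only if the list has not been generated. Protocol 5.2 describes meal changes made after participant feedback in the past tense, so it may be too late. It is also a trade-off: with 75% women and an assumed 60% treated, untreated men would number 45 × 0.25 × 0.40 = 4.5. Blocks would have to be small and some would stay incomplete.
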